6.2. Handling of Dropouts or Missing Data

Missing data, except dates, will not be imputed. Historical data such as historical diagnosis, historical illness, preexisting conditions, and prior therapies should be collected in a sufficiently informative way. For example, in order to be considered as historical illness, events occurring in the same year as study entry should have at least a known month and year for the end date, while events occurring in previous years should have at least a known year for the end date. When dates need to be imputed, missing days will be replaced with 15th of the month and missing day/month with 01 July.

In the following situations of Part A, patients will be considered nonevaluable and may be replaced to ensure that enough patients complete 1 cycle of therapy at each dose level, unless accrual to that cohort has stopped due to a DLT:

1. Any patient who is discontinued from the study before completing 1 cycle of therapy unless they experience a DLT prior to withdrawal
2. Patients who are not evaluable for PK, but who complete 1 cycle of therapy

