The interpretation of the study results will be the responsibility of the investigator with the sponsor's CRP/CRS, PK scientist and statistician. The sponsor's CRP/CRS and statistician will also be responsible for the appropriate conduct of an internal review for both the final study report and any study-related material to be authorized by Lilly for publication. The analyses for this study will be descriptive; no p values will be calculated. Data analyses will be provided by cohort and treatment, whenever appropriate. For continuous variables, summary statistics will include number of patients, mean, median, standard deviation, minimum, and maximum. Categorical endpoints will be summarized using number of patients and percentages. Missing data will not be imputed.

Exploratory analyses of the data not described in Sections 10.2 through 10.9 will be conducted as deemed appropriate.

A detailed description of data analyses will be provided in a separate statistical analysis plan document for this study.

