4.1. Primary Objectives

The primary objectives of this study are:

- to characterize the safety profile and tolerability of each combination, LY3022855 with durvalumab (MEDI4736) and LY3022855 with tremelimumab, in the treatment of patients with advanced solid tumors
- to define a recommended Phase 2 dose (RP2D) for each combination, LY3022855 with durvalumab and LY3022855 with tremelimumab, in the treatment of patients with advanced solid tumors

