6.8.3. Adverse Events

Adverse event terms and severity grades will be assigned by the investigator using CTCAE v4. Any minor version of CTCAE v4 (for example, CTCAE Version 4.03) may be used for this study. In addition, AE verbatim text will also be mapped by the sponsor or designee to corresponding terminology within the Medical Dictionary for Regulatory Activities (MedDRA®) dictionary. Adverse events will be reported using a unified CTCAE/MedDRA reporting process:

- The CTCAE v4.0 term reported by the investigator will be mapped to the MedDRA preferred term (PT) and system organ class (SOC) of the corresponding MedDRA lowest level term (LLT), unless the reported CTCAE term is “Other-specify”.
- If the reported CTCAE term is “Other-specify” the MedDRA LLT, PT, and SOC mapped from the verbatim AE term will be used.
- All listings and summaries will use the CTCAE terms when available or the MedDRA LLT, along with the MedDRA PT resulting from this process.

A treatment-emergent adverse event (TEAE) is defined as any AE that begins on or after the day of the first dose of study treatment or any preexisting condition that increases in CTCAE grade on or after the day of the first dose of study treatment. Comparisons of preexisting conditions to on-treatment events at the LLT level will be used in the treatment-emergence computation.

The number of patients who experienced a TEAE, serious adverse event (SAE), or TEAE possibly related to study drug will be summarized. TEAEs will be summarized by SOC, by PT terms of decreasing frequency within SOC, and by maximum CTCAE grade and grade categories. Immune-related AEs may be tabulated if deemed appropriate.

Historical illnesses are defined as events that ended before completion of the screening visit. Preexisting conditions are defined as AEs that begin but do not resolve prior to the administration of the first dose of study drug. The preexisting conditions will be presented by patient and can be combined with the AE listing, so that the history of the preexisting conditions/AEs can be traced. Historical illnesses and preexisting conditions will be summarized and listed by cohort and overall for all patients on therapy.

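### The SAP's 15th-of-month / 1 July date rule has no floor at first dose, so adverse events with partial onset dates can be misclassified as to treatment emergence, including loss of true TEAEs

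*SAP*

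**What the plan says.** SAP 6.2 opens with a general statement: "Missing data, except dates, will not be imputed". After some sentences on historical diagnoses, illnesses, preexisting conditions and prior therapies, it gives the only date rule in either document: "missing days will be replaced with 15th of the month and missing day/month with 01 July". There is no separate rule for AE onset and no reference to the first-dose date.

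SAP 6.8.3 makes a new event a TEAE by its onset date: "any AE that begins on or after the day of the first dose of study treatment". Something already present before treatment qualifies only by worsening, under a second limb of the definition. The same section states: "Preexisting conditions are defined as AEs that begin but do not resolve prior to the administration of the first dose of study drug". The main AE output rests on this classification: "TEAEs will be summarized by SOC, by PT terms of decreasing frequency within SOC, and by maximum CTCAE grade and grade categories". Those tables serve the first primary objective in SAP 4.1, "to characterize the safety profile and tolerability of each combination".

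The TEAE flag is also used in the annual-report summaries (SAP 6.17) and in the registry analyses (SAP 6.18), where a non-serious event is counted only if it is a TEAE.

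Protocol 10.1, like the synopsis, says: "Missing data will not be imputed". It makes no exception for dates.

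**The concern.** A patient first dosed late in a month, with an AE onset recorded only to that month, is given an onset on the 15th, before treatment. The event is then not a TEAE. If it is unresolved at first dose it meets the definition of a preexisting condition, and it returns to the TEAE tables only if its grade later rises. A non-serious event also leaves the registry's other-AE table. Nothing else in the SAP or protocol prevents this.

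At stake is whether the tables that answer the primary safety objective classify early events correctly. In Part B cohorts of about 20 patients, one reclassified event is visible in a reported rate. The SAP and protocol also differ on whether dates may be imputed at all.

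**Working it through.** The plan states no figure on date imputation, so there is none to reproduce. The scale check in step 7 uses the exact intervals of Table JSCC.5.1; its entry for 5 of 20 reproduces (0.087 to 0.491, printed as 0.09 to 0.49).

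**Inputs.** The imputation rule (SAP 6.2); the TEAE rule (SAP 6.8.3); a 28-day Cycle 1 (Protocol 6.2); about 20 patients per Part B cohort (SAP 5.1).

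**Assumptions, not in the documents.** First dose is equally likely on each day of a 365-day year (seven months of 31 days, four of 30, one of 28). True onset is uniform over the first W days from first dose. The onset day is missing.

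1. **One case.** First dose 20 March, true onset 24 March, recorded as March. Imputed onset is 15 March, 5 days before first dose: not a TEAE.

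2. **When it happens.** The imputed 15th precedes first dose only if first dose is on the 16th or later and onset is in that same month. Such first-dose days number 7×16 + 4×15 + 13 = 185, and 185/365 = 50.7%.

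3. **Share of same-month onsets lost.** In a month of L days there are L(L+1)/2 pairs of first-dose day and same-month on-treatment onset day: 496, 465 and 406 for L = 31, 30 and 28. Total: 7×496 + 4×465 + 406 = 5738. Lost pairs number (L−15)(L−14)/2: 136, 120 and 91. Total: 7×136 + 4×120 + 91 = 1523. Share: 1523/5738 = 26.5%.

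4. **Share by onset window.** Every lost onset lies within 16 days of first dose, so for W of 16 or more the share is 1523/(365×W).
   - W = 28 (Cycle 1): 1523/10220 = 14.9%
   - W = 84: 1523/30660 = 5.0%
   - W = 168 (six cycles): 1523/61320 = 2.5%
   - For the first 7 days alone, enumeration gives 40.8%, so the loss is concentrated early.

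5. **The reverse error.** Pre-dose onset days in the first-dose month number L(L−1)/2: 465, 435 and 378, in total 7×465 + 4×435 + 378 = 5373. For first doses on the 1st to the 15th, the imputed 15th falls on or after first dose. That moves 0+1+…+14 = 105 pairs per month, and 12×105 = 1260. Share: 1260/5373 = 23.5%. Over the 28 days before first dose it is 1260/10220 = 12.3%.

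6. **Day and month both missing.** Onset becomes 1 July, so any AE in the same year as a first dose after 1 July is lost. Enumeration gives 46.4% for onset within 28 days and 27.3% within 168 days, if such a date arises.

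7. **Scale.** If q is the share of Cycle 1 AEs with a missing onset day, the fraction of all Cycle 1 AEs lost is q×14.9%. The documents do not give q. For illustrative values of 1% to 10% the result is 0.15% to 1.5%. In one 20-patient cohort, losing 1 of 5 cases moves the estimate from 25% (9% to 49%) to 20% (6% to 44%).

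8. **With a floor.** Setting onset to the later of the imputed date and first dose, when the known part of the date matches that of first dose, reduces the loss to 0 (checked for W = 28 and 168).

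**The case against.** **The rule may be meant for historical data.** It closes a paragraph on historical data and applies only where dates need imputing. That is fair evidence of intent. But the paragraph's first sentence is general, and no other rule covers AE dates, so a programmer would have only this one to apply.

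**Partial on-treatment onsets should be rare.** Protocol Attachment 1 schedules AE grading on Days 1, 8, 15 and 22 of each cycle, Protocol 8.1.2.1 requires notification of serious events within 24 hours, and Protocol 9.1 plans edit and source checks. This stands. It makes a year-only on-treatment onset implausible and keeps the overall effect small.

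**The events do not vanish.** Preexisting conditions are summarised and listed and can be combined with the AE listing (SAP 6.8.3). Dose-limiting toxicities are summarised separately (6.8.2), deaths and serious events are listed (6.8.4), laboratory grades are derived from the values (6.8.5), and registry serious events count regardless of TEAE status (6.18). This also stands. What remains exposed is non-serious toxicity that is not dose-limiting.

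**The protocol conflict is slight.** The sentence in Protocol 10.1 ends a description of summary statistics, and the section defers detail to the SAP. That makes it a wording mismatch to reconcile, not a breach.

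**Stronger readings a reader might infer.** One is that the rule biases toxicity downward. The documents do not support that: step 5 shows a reverse error of similar relative size, and the net direction depends on how many partially dated events lie on each side of first dose, which is not given. Another is that progression dates are distorted in the same way. Progression in SAP 6.13 is objective and rests on scheduled scans, and nothing shows that partial progression dates would arise.

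**Conclusion.** The point holds as misclassification of treatment emergence, including loss of true TEAEs; net understatement of toxicity is not shown. With only the day missing, it is confined to first doses on the 16th or later with onset in the same calendar month. That is 26.5% of all onsets in the first-dose month, 14.9% of onsets in Cycle 1 and 2.5% over 168 days. All these figures are conditional on a partial date and on uniform first-dose and onset days. The frequency of partial dates is unknown and probably low, so the expected effect on the tables is small. It still merits correction, because the stated rule gives a wrong answer in a foreseeable case, in the tables for the primary objective, and the remedy is cheap.

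**What to change.** In SAP 6.2:

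- Keep the 15th / 1 July rule for historical data.
- Add a rule for AE onset. Impute a partial date in the same way, but if its known part (month and year, or year alone) matches that of first dose, use the later of the imputed date and the first-dose date. The exception is where the AE end date or other recorded information shows that the event began or ended before first dose. An imputed onset may not fall after the end date. Say that this means a recorded end date, since an end date itself imputed to the 15th proves nothing.
- Optionally, state that a partial death date is not imputed earlier than the last date known alive. No rule for progression dates is needed.

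In Protocol 10.1 and the synopsis, except partial dates from the statement on missing data.

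The cost is a few lines of text and programming. The SAP needs revision in any case: its sections 5 and 5.1 still plan five Part B cohorts and up to about 178 patients, against two cohorts and about 118 in the current protocol. The downside is that a few pre-dose events with ambiguous dates may be counted as TEAEs, so TEAE counts may rise slightly.

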6.3. Population for Analysis

Safety and efficacy analyses will be conducted on all patients who have received at least 1 dose of the study treatment(s), regardless of whether they are deemed evaluable for the assessment of a dose level.

Pharmacokinetic (PK) analyses will be conducted on patients who have received at least 1 dose of the study treatment(s) and have sufficient samples collected to allow the estimation of LY3022855, durvalumab, and tremelimumab PK parameters.

Pharmacodynamic (PD) analyses will be conducted on subjects who have received at least 1 dose of the study treatment(s) and have sufficient samples collected to allow the assessment of PD.

6.4. Patient Disposition

A detailed description of patient disposition will be provided. It will include summaries of the number and percentage of patients entered into the study, enrolled in the study, and completing the study (with data indicating completion of study primary and secondary objectives in electronic case report form page of the End of Study), and reasons for discontinuation from study treatment, as well as discontinuation from the study. All patients entered in the study will be included in the summary. Reason for discontinuation from both study treatment and the study will be listed by the pre-determined categories. If the reason for discontinuation is AE or death, the associated AE or cause of death will be reported.

6.5. Patient Characteristics

Patient characteristics will be summarized and listed for all patients enrolled and will include:

- patient demographics, including age, sex, race, ethnicity, screening height and weight, and screening body mass index

- baseline disease characteristics, including initial pathological diagnosis, basis for initial diagnosis, disease stage at initial diagnosis, and Eastern Cooperative Oncology Group performance status (PS)
- prior disease-related therapies, including systemic, radiotherapy, and cancer surgeries, if known, including dose, best response, and date of progression
- historical substance consumption, such as alcohol and tobacco use

Other patient characteristics will be summarized and listed as deemed appropriate.

6.6. Treatment Compliance

LY3022855, durvalumab, and tremelimumab will be administered intravenously at the investigational site under the direction of the investigator. As a result, a patient's compliance with study drug administration is ensured.

6.7. Concomitant Therapy

All medications will be coded to the generic preferred name according to the current World Health Organization drug dictionary. All concomitant medications will be listed and summarized using the preferred name by cohort and overall for all patients on therapy.

6.8. Safety Analyses

All patients who receive at least 1 dose of LY3022855, durvalumab, or tremelimumab will be evaluated for safety and toxicity. The National Cancer Institute Common Terminology Criteria for Adverse Events Version 4.0 (NCI-CTCAE v4.0) will serve as the reference document for choosing appropriate terminology for, and grading the severity of, all AEs and other symptoms.

Safety analyses will include summaries of the following:

- AEs, including severity and possible relationship to study drug
- DLTs at each dose level
- dose adjustments
- laboratory values
- vital signs
- electrocardiogram (ECG) readings
- transfusions

6.8.1. Extent of Exposure

Study drug exposure information will be summarized by cohort and overall for patients on therapy, including cycles received per subject, duration on therapy, and cumulative dose.

Dose adjustments, including the reasons for dose adjustment, will also be listed, and will be summarized by cohort and overall for patients on therapy.

Dose intensity, defined as the actual amount of drug taken per week, and relative dose intensity, defined as the actual amount of drug taken/planned amount of drug taken $\times 100\%$, will also be summarized by cohort and overall.

6.8.2. Dose-Limiting Toxicity

Dose-limiting toxicities (DLTs) during Cycle 1 (the DLT-evaluation period) in Part A will be summarized and listed by cohort and overall if appropriate.

DLT-equivalent toxicities will also be summarized and listed by cohort and overall for the safety population.

6.8.3. Adverse Events

Adverse event terms and severity grades will be assigned by the investigator using CTCAE v4. Any minor version of CTCAE v4 (for example, CTCAE Version 4.03) may be used for this study. In addition, AE verbatim text will also be mapped by the sponsor or designee to corresponding terminology within the Medical Dictionary for Regulatory Activities (MedDRA®) dictionary. Adverse events will be reported using a unified CTCAE/MedDRA reporting process:

- The CTCAE v4.0 term reported by the investigator will be mapped to the MedDRA preferred term (PT) and system organ class (SOC) of the corresponding MedDRA lowest level term (LLT), unless the reported CTCAE term is “Other-specify”.
- If the reported CTCAE term is “Other-specify” the MedDRA LLT, PT, and SOC mapped from the verbatim AE term will be used.
- All listings and summaries will use the CTCAE terms when available or the MedDRA LLT, along with the MedDRA PT resulting from this process.

A treatment-emergent adverse event (TEAE) is defined as any AE that begins on or after the day of the first dose of study treatment or any preexisting condition that increases in CTCAE grade on or after the day of the first dose of study treatment. Comparisons of preexisting conditions to on-treatment events at the LLT level will be used in the treatment-emergence computation.

The number of patients who experienced a TEAE, serious adverse event (SAE), or TEAE possibly related to study drug will be summarized. TEAEs will be summarized by SOC, by PT terms of decreasing frequency within SOC, and by maximum CTCAE grade and grade categories. Immune-related AEs may be tabulated if deemed appropriate.

Historical illnesses are defined as events that ended before completion of the screening visit. Preexisting conditions are defined as AEs that begin but do not resolve prior to the administration of the first dose of study drug. The preexisting conditions will be presented by patient and can be combined with the AE listing, so that the history of the preexisting conditions/AEs can be traced. Historical illnesses and preexisting conditions will be summarized and listed by cohort and overall for all patients on therapy.

6.8.4. Deaths, Other Serious Adverse Events, and Other Notable Adverse Events

A summary of deaths will be presented by cohort and overall. Reasons for death will be summarized separately for deaths on therapy, within 30 days of discontinuation of study therapy (counting from the date the decision to discontinue treatment is made) and after 30 days of discontinuation of study therapy. Other listings include:

- Listing of Deaths
- Listing of Serious Adverse Events
- Listing of Subjects who Discontinued due to Adverse Events of Death

6.8.5. Clinical Laboratory Evaluation

Laboratory data (including abnormal laboratory data) will be listed by cycle for all patients on therapy. In addition to the investigator-reported AEs, relevant hematology and chemistry laboratory values will be graded according to CTCAE v4.0. These abnormal lab parameters with derived CTCAE grades will be summarized by visit and cohort.

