The key toxicological findings attributed to LY3022855 administration in preclinical studies included reversible mild-to-moderate increases in serum transaminases (AST and alanine aminotransferase [ALT]) and target organ effects in liver (Kupffer cell hypertrophy/hyperplasia). No histological changes in the liver were noted to correlate with the transaminase increases, nor were any changes noted in liver functional parameters (that is, alkaline phosphatase, bilirubin, or coagulation). Therefore, based on the small magnitude of the elevations and their limited impact to the overall health of the animal, the increases in ALT and AST were not considered adverse. The effect on Kupffer cells, specialized macrophages in the liver that play an important role in the clearance of several serum enzymes, including AST and CK, was regarded as immunomodulatory and was possibly associated with elevations in circulating CSF-1 levels.

In clinical studies of LY3022855 monotherapy, increases in serum AST and CK levels (mostly Grades 1 and 2) were noted in 19 and 17 patients, respectively, who received LY3022855 (of the total 64 patients) as of 28 January 2017. The majority of these patients experienced elevations in both enzymes and received 1.25 mg/kg Q2W, 2.5 mg/kg QW, 100 mg QW, or 150 mg QW of LY3022855. One case of a dose-limiting adverse event (AE) of Grade 4 rhabdomyolysis leading to Grade 4 acute renal failure was reported in a patient treated with LY3022855 1.25 mg/kg QW. The patient recovered from the events following discontinuation of study treatment. One of the 3 patients administered the dose of 150 mg QW experienced a Grade 3 CK elevation with associated elevated levels of serum and urine myoglobin. Although no similar observations were noted in additional 3 patients, the dose of 100 mg QW was selected as the recommended Phase 2

dose for LY3022855 due to potential safety issues related to the QW dosing of 150 mg as evidenced by the laboratory abnormalities induced by LY3022855. None of the patients with increased levels of AST experienced clinical symptoms suggestive of hepatic toxicity, nor were elevations of bilirubin noted at the time of the AST elevations. Among all patients with AST and CK elevations, only 1 patient who received the dose of 2.5 mg/kg QW of LY3022855 was discontinued from the study due to drug-related increases in CK (Grade 3), AST (Grade 3), and lactate dehydrogenase (LDH; Grade 1).

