8.1.2. Adverse Events

Lilly has standards for reporting AEs that are to be followed regardless of applicable regulatory requirements that may be less stringent. A clinical study AE is any untoward medical occurrence in a patient or clinical investigation patient administered a pharmaceutical product and which does not necessarily have a causal relationship with this treatment. An AE can therefore be any unfavorable and unintended sign (including an abnormal laboratory finding), symptom, or disease temporally associated with the use of medicinal (investigational) product, whether or not related to the medicinal (investigational) product. Any clinically significant findings from labs, vital signs measurements, and so on that occur should also be reported to Lilly or its designee as an AE. Lack of drug effect is not an AE in clinical studies because the purpose of the clinical study is to establish drug effect.

The investigator, monitor, and sponsor will review the collected data regularly for evidence of AEs. All patients will be assessed routinely for AEs as outlined in the study schedule. All AEs observed will be graded using CTCAE v4.0.

The NCI-CTCAE v4.0 will serve as the reference document for choosing appropriate terminology for, and grading the severity of, all AEs and other symptoms. All AEs observed will be graded using CTCAE v4.0. Any minor version of CTCAE v4.0 (for example, version 4.03) may be used for this study. Minor CTCAE v4.0 updates from the NCI will not necessitate a protocol amendment. For AEs without matching terminology within the NCI-CTCAE v4.0 criteria, the investigator will be responsible for selecting the appropriate system organ class and assessing severity grade based on the intensity of the event. Note that both CTCAE term (actual or coded) and severity grade must be selected by study site personnel and collected on the eCRF. This collection is in addition to verbatim text used to describe the AE.

In addition to collecting the AE verbatim, the CTCAE term, and the CTCAE severity grade, AE verbatim text will also be mapped by the sponsor or designee to corresponding terminology within the Medical Dictionary for Regulatory Activities (MedDRA) dictionary.

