8.2.1. Samples for Study Qualification and Health Monitoring

Blood, tissue, and urine samples will be collected to determine whether patients meet inclusion/exclusion criteria.

Standard laboratory tests, including hematology and urinalysis panels, will be performed and analyzed by a local laboratory. Chemistry panels will be performed and analyzed centrally. Enrollment decisions may be based upon chemistry results performed at a local laboratory; however, a sample must be sent to the central laboratory. These central chemistry laboratory results will be used for subsequent safety analyses. In the event of minor discrepancies between local and central laboratory results, the investigator may use the local results for treatment decisions, and the central laboratory results will remain part of the safety database. Discrepancies between local and central results that may have an impact on treatment decisions will not be considered protocol violations.

Investigators must document their review of each laboratory safety report.

Samples collected for specified laboratory tests will be destroyed within 60 days of receipt of confirmed test results. Tests are run and confirmed promptly whenever scientifically appropriate. When scientific circumstances warrant, however, it is acceptable to retain samples to batch the tests run, or to retain the samples until the end of the study to confirm that the results are valid. Certain samples may be retained for a longer period, if necessary, to comply with applicable laws, regulations, or laboratory certification standards.

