	
Hold treatment with both LY3022855 and durvalumab or tremelimumab. Perform diagnostic evaluation.
 
 For Grade 3 elevations in CK \leq 8X ULN with a diagnostic evaluation showing NO evidence of end organ damage including myositis or rhabdomyolysis, resume treatment with both agents. For Grade 3 elevations in CK $>$ 8X ULN with a diagnostic evaluation showing NO evidence of end organ damage including myositis or rhabdomyolysis, hold LY3022855 and resume durvalumab or 	
 Perform diagnostic evaluation (serum and urine myoglobin, BUN and creatinine). Continue to monitor CK, serum and urine myoglobin, BUN and creatinine Weekly until CK levels return to \leq Grade 1 or as clinically indicated. Treat accordingly as per institutional standard, perform a full diagnostic evaluation and if there is any evidence of potential immune-mediated end organ damage, follow the guidelines for irAE management contained in this attachment.

Non-Immune-Mediated Reactions

Severity Grade of the Event (NCI CTCAE version 4.03)	Dose Modifications	Toxicity Management
	
tremelimumab after discussion with sponsor.
 
If CK decreases to $\leq 8x$ ULN after holding LY3022855, resume treatment with LY3022855 and durvalumab or tremelimumab.
 
 ○ If CK remains $>8X$ ULN after holding LY3022855, permanently discontinue both LY3022855 and durvalumab or tremelimumab and discuss additional treatment measures with sponsor. 
In case of myositis or rhabdomyolysis, permanently discontinue treatment with both study agents.
	
 ● Continue to monitor CK, serum and urine myoglobin, BUN and creatinine weekly until CK levels return to \leq Grade 1 or baseline.
Grade 4	
Discontinue study drug/study regimen (Note: For Grade 4 labs, decision to discontinue should be based on accompanying clinical signs/symptoms, the Investigator's clinical judgment, and consultation with the Sponsor.).
	Treat accordingly, as per institutional standard.

Note: As applicable, for early phase studies, the following sentence may be added: "Any event greater than or equal to Grade 2, please discuss with Study Physician."

Abbreviations: AE = Adverse event; BUN = elevated serum blood urea nitrogen; CK = creatinine; CTCAE = Common Terminology Criteria for Adverse Events;

NCI = National Cancer Institute.

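### SAP 6.8.5 tabulates lab-derived CTCAE grades only by visit, so it does not show how many patients ever reached each grade of CK, AST, ALT or bilirubin elevation

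*SAP*

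**What the plan says.** SAP 6.8.5 grades relevant hematology and chemistry values by CTCAE, in addition to the adverse events that investigators report, and then states: "These abnormal lab parameters with derived CTCAE grades will be summarized by visit and cohort". Individual values are also listed: "Laboratory data (including abnormal laboratory data) will be listed by cycle for all patients on therapy". The section names no worst post-baseline grade, no shift from baseline and no count of patients ever elevated. Protocol 10.4 adds only that laboratory values will be summarized.

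Three other parts of the SAP count patients. Section 6.8.3 says: "TEAEs will be summarized by SOC, by PT terms of decreasing frequency within SOC, and by maximum CTCAE grade and grade categories". Section 6.8.2 says: "Dose-limiting toxicities (DLTs) during Cycle 1 (the DLT-evaluation period) in Part A will be summarized and listed by cohort", and also covers DLT-equivalent toxicities. Section 6.8.1 summarizes dose adjustments with their reasons.

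On which chemistry is analyzed, Protocol 8.2.1 says: "These central chemistry laboratory results will be used for subsequent safety analyses". The schedule in Protocol Attachment 1 also has local chemistry that must be reviewed before each dose.

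**The concern.** The study's primary safety objective needs the number of patients affected at each dose level. The sample-size argument for Part B (Protocol 10.1, SAP 5.1) is also framed as a patient-level incidence in 20 patients. A by-visit table answers a different question: what share of those sampled were abnormal on that occasion.

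This matters most for CK and AST. Protocol 5.1.2 reports from LY3022855 monotherapy that "increases in serum AST and CK levels (mostly Grades 1 and 2) were noted in 19 and 17 patients" out of 64. Such rises have shaped dosing without being DLTs. Protocol 5.4.1 describes Grade 2 to 3 CK or AST elevations in 5 of the 6 patients at the first dose studied. None was classed as a DLT, yet escalation was restarted lower. Protocol 5.1.2 gives laboratory abnormalities as the reason for the monotherapy dose recommendation. In both cases the count of affected patients per dose level was the relevant quantity.

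The adverse event table depends on judgement for these analytes. Protocol 8.1.2 says: "Any clinically significant findings from labs, vital signs measurements, and so on that occur should also be reported". Protocol 5.1.2 itself argues that these enzyme rises do not necessarily indicate organ damage, so an investigator may reasonably leave an asymptomatic rise unreported.

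**Working it through.** **The plan's own figure.** SAP Table JSCC.5.1 gives Clopper-Pearson limits for a patient-level incidence with n = 20. Recomputed from beta quantiles: 0/20 gives 0 to 0.168; 5/20 gives 0.087 to 0.491; 10/20 gives 0.272 to 0.728; 15/20 gives 0.509 to 0.913. All agree with the table and are not in dispute. They show that the intended quantity is patients with an event.

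**Inputs.**
- Earlier patient-level rates (Protocol 5.1.2): AST 19/64 = 0.297 (exact 95% CI 0.189 to 0.424); CK 17/64 = 0.266 (0.163 to 0.391). That these apply to the combinations is an assumption.
- Scheduled central chemistry after the first dose in Cycles 1 and 2 (Protocol Attachment 1): Cycle 1 Days 2, 8, 15 and 22, and Cycle 2 Days 1, 8, 15 and 22, so k = 8 draws. The Cycle 1 Day 1 sample is taken before infusion and is a baseline value.

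**From patients to visits.** Let p be the proportion of patients ever elevated, and suppose each is abnormal at m of k draws with everyone attending. The average by-visit rate is p × m/k.
- m = 1: AST 0.297 × 1/8 = 0.037; CK 0.266 × 1/8 = 0.033.
- m = 2: AST 0.297 × 2/8 = 0.074.
- m = 8: AST 0.297; CK 0.266.

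In a 20-patient cohort, about 5.9 patients with AST elevation (20 × 0.297) could appear as an average of 0.74 per draw (5.9/8) or as 5.9 at every draw.

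**If visit means a cycle.** Attachment 1 labels the whole of Cycle 1 as Visit 1. Cycles 1 and 2 then hold two visits, and the average is at least 0.297/2 = 0.148. The range becomes 14.8% to 29.7%.

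**From visits back to patients.** A rate q at each of k visits fits any patient-level incidence from q (the same patients each time) to the smaller of 1 and k × q (different patients each time). For k = 8, q = 5% fits 5% to 40%, and q = 10% fits 10% to 80%. The by-visit table therefore cannot be converted into an incidence.

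**Which rises the other tables miss.**
- Protocol 7.2.2.1 excludes from DLTs an asymptomatic Grade 3 CK without raised myoglobin or muscle injury, and an isolated asymptomatic Grade 3 AST. The CK exclusion (5 to 10 × ULN) overlaps the CK DLT criterion (above 8 × ULN); those two lines need reconciling.
- Attachment 7 continues dosing through an isolated asymptomatic Grade 2 AST, so no dose adjustment arises. It also requires no dose modification for laboratory abnormalities deemed not clinically significant.
- If such a rise is also not reported as an adverse event, it appears only in the by-visit summary and the listings.

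**Baseline.** Inclusion criterion 7 allows AST and ALT up to 5 × ULN with liver metastases, while Attachment 7 grades values above 3 and up to 5 × ULN as Grade 2. Some patients can enter already at Grade 2, so transaminase grades need to be read against baseline. Exclusion criterion 27 bars a raised CK at entry, so for CK the shift adds little beyond the worst grade.

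**The case against.** The strongest reply is that patient-level tables already exist. A reader might infer from SAP 6.8.5 alone that no table gives the incidence or peak grade of CK and AST elevation. That goes too far. Adverse events are tabulated by maximum grade, DLTs and DLT-equivalent toxicities by cohort, and dose adjustments with reasons. Attachment 7 directs a hold even for asymptomatic Grade 2 CK. The adverse event definition in Protocol 8.1.2 expressly includes abnormal laboratory findings, and every value is listed. This stands and narrows the gap to unreported rises.

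A reader might also infer a 4- to 8-fold understatement, from 29.7% against 7.4% or 3.7%. That holds only if each elevation lasts one or two draws and a visit is a sampling day. Protocol 5.4.1 says enzyme levels fell after LY3022855 was stopped, which is at least compatible with persistence during dosing. With full persistence there is no understatement.

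Unscheduled samples are a smaller issue than they look. Attachment 7 says: "Continue to monitor CK, serum and urine myoglobin, BUN and creatinine", weekly. Central chemistry is already scheduled weekly through Cycle 4, so the schedule becomes sparser than that monitoring only from Cycle 5. The SAP does not say that unscheduled results are excluded; it gives no rule.

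Finally, using one central laboratory is a sound choice for consistency. Protocol 8.2.1 allows local results for treatment decisions where discrepancies are minor, and a DLT is counted whichever laboratory produced the value. Taking the worse of two duplicate measurements would push grades upward. What remains is that no rule covers a local value that drove a hold or DLT and has no central counterpart.

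**Conclusion.** The concern holds in a limited form. The only planned summary of lab-derived grades is by visit and cohort, and it cannot show how many patients ever reached each grade. Elevations reported as adverse events, DLTs, DLT-equivalent toxicities or reasons for dose adjustment are counted per patient elsewhere. Those judged not clinically significant and left unreported are not.

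The size is not determined. With p = 29.7% and eight draws, the by-visit average lies between 3.7% and 29.7%; with a visit read as a cycle, between 14.8% and 29.7%. Both ranges assume that the monotherapy rate carries over and that all patients attend every draw. How many elevations would go unreported cannot be estimated from the documents.

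The documents also do not support calling CK and AST elevation the drug's main toxicity. They show it to be frequent and ask for close monitoring, but the DLTs reported in Protocol 5.4.1 were left ventricular dysfunction, pancreatitis and rhabdomyolysis.

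The change is worth making because it is cheap and serves the primary objective. The SAP was approved in April 2016, before Amendment (b), which cites January 2017 data and revised the DLT criteria for these enzymes. SAP 6.8.5 should be checked against the current criteria in any case.

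**What to change.** In SAP 6.8.5:

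1. Add, by regimen and cohort, a table of baseline grade against worst post-baseline grade per patient for CK, AST, ALT and total bilirubin. Use all scheduled and unscheduled central results, with all treated patients as the denominator. Show patients without a post-baseline value in their own column.
2. Keep the by-visit table as secondary, and state whether a visit is a sampling day or a cycle.
3. Where a local chemistry value led to a hold or DLT and no matching central value exists, show it in a flagged sensitivity table. Do not take the worse of local and central values in the main table.

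The cost is SAP wording, one extra standard table and a small sensitivity table. The local values in item 3 must be entered in the eCRF if they are not already captured.
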